We will assess the consistency of the GDM causal mechanisms with a repeat OGTT two weeks after treatment initiation, adherence to treatment assignment and dose titration, and the distribution of adipose-related metabolism covariates (e.g. obesity, lipid profile, free fatty acids). This data will be used to inform the study design, data collection procedures and outcomes measures of the large-scale RCT.

Aim 3. Assess participant and provider acceptability of an RCT comparing individualized GDM treatment and usual care.

We will conduct individual semi-structured interviews with 3 groups: (1) pilot participants (n=16), to determine acceptability and burden of the study; 2) prenatal care providers (n=15) to determine their satisfaction with study procedures, and 3) women who are approached but decline to participate in the pilot study (n=15) to determine barriers to participation.

III. PARTICIPANTS

Inclusion criteria:

Pregnant women 18-45 years old, beyond 24 weeks of gestation, who are scheduled for a 3-hour oral glucose tolerance test.

Exclusion criteria:

- Preexisting type 1 or type 2 DM
- Multiple gestation
- GDM diagnosis without 3-hour OGTT
- Oral or IV corticosteroid use in the past 7 days
- Major congenital anomaly with anticipated preterm delivery
- Allergy to glyburide, metformin or sulfa
- History of severe pulmonary disease(pulmonary requirement for oxygen therapy or daily treatment for restrictive or obstructive pulmonary disease)
- History of hepatic disease (LFT's greater than two times of upper normal range)
- History of renal disease (serum creatinine higher than 1.2 mg/dL)
- History of heart failure or myocardial infarction

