Participants are eligible to be screened if they have scheduled a 3-hour oral glucose tolerance test, as recommended by their primary physician. Her medical records will be reviewed and she will be asked questions about her medical history, physical examinations, laboratory tests, and medications to make sure she is eligible for the study. She will be instructed on procedures to follow for the upcoming study visits. This screening visit will be performed by a member of the research team at the time of the scheduled 3-hour oral glucose tolerance test. It is not expected to prolong the time of the clinical test.

The 3-hour oral glucose tolerance test is usually performed following an abnormal glucose screen during pregnancy. After completion of the consent form, subjects will undergo a standard oral glucose tolerance test in the outpatient laboratory unit. Samples will be collected at 0, 1, 2 and 3 hours after ingesting a 100g oral glucose load. A standard oral glucose tolerance test includes blood collection for glucose determination at 0, 1, 2, and 3 hour after ingestion of a 100g oral glucose load (3mL x4 = 12mL total). The study will include additional sample collection at the initial time point (0 hour) for lipid (6mL), and at 0, 1, 2 and 3 hour for insulin and c-peptide (3 mL x4 = 12 mL) determination.

Additionally, anthropometric measures including triceps, subscapular and suprailiac skin fold thickness will be performed.

Materials needed per participant

- **Four** red top tubes for plasma samples (Insulin, C-peptide, free fatty acids)
- **One** green top sodium heparin or lithium heparin tube for serum samples (lipid panel)
- Lange skinfold caliper

1. Blood Samples During screening visit (Table 1)

Time Intervals (in mins)	Insulin; C-peptide, free fatty acids,	Lipids
Tube top	Red	Green
0	X	X
60	X	
120	X	
180	X	

a. At time 0 (c-peptide, insulin, free fatty acids, and lipids)

- Fill a pre-prepared red top tube with 4 mL of blood (insulin, c-peptide, free fatty acids)
 1. Gently invert tube five times to avoid clotting
 2. Place sample on ice
 3. Centrifuge sample at 1200 RFG (approximately 3000rpm) at 4°C for 15 minutes

- Fill a pre-prepared light green top tube with 4 mL of blood (lipids)
 1. Gently invert tube five times to avoid clotting
 2. Place sample on ice
 3. Centrifuge sample at 1200 RFG (approximately 3000rpm) at 4°C for 15 minutes

b. At times **60, 120 and 180** (c-peptide, and insulin)

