Time Intervals (in mins)	Glucose	Insulin; C-peptide, free fatty acids,	Lipids
Microvial	Grey	Red	Green
0	1	2	1
60	1	2	
120	1	2	
180	1	2	

Interviews will occur at the time of the second OGTT for women who are enrolled in the study and at the time of refusal for those who opt out. Interviews will focus on participant/provider perception of study/treatment and whether they experienced any burdens. 16 participants (8 in each group) will be interviewed along with 10 women who decline to enroll in the study but agree to an interview.

Additional study visits:

During a participant's routine prenatal visits (which typically occur every 1-2 weeks) with her provider that occur between 29 and 40 weeks of gestation, she will also meet with a member of the research team who will record information about her blood glucose measurements, pregnancy, weight, and any side effects she had since the last study visit. These study visits will occur in her provider's office and will take no more than 10 minutes to complete.

At the time of labor and delivery

Delivery: At delivery, the hospital research nursing team we will measure infant birth weight and length at delivery. We will collect umbilical cord venous blood for assay of c-peptide. We will only collect these samples if it is safe to do so and possible to do so based on staffing.

Air displacement plethysmography will be used to measure body composition (PEA POD; Life Measurement Inc, Concord, CA) in the newborns within 72 hours post-delivery to provide an estimate of percent body fat and lean body mass.

Data abstraction: Once written consent is provided and participant completes the first study visit, a member of the research team will conduct at least two prenatal and two postnatal EHR data abstraction from the prenatal and delivery records: type of delivery, prenatal and delivery complications. We will also collect information regarding any treatment for gestational diabetes as well as the number of ultrasounds and tests for assessment of fetal well-being (biophysical profiles, non-stress tests).

VIII. Participant withdrawal:

Participants may withdraw from the study at any time.

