(If Yes): Before enrolling people in this study, we need to determine if you meet the eligibility criteria. If it is alright with you, I would like to ask you a series of questions. You do not have to answer these questions, and you need to know the purpose of these questions is only to determine whether you are eligible for this study. All information that I receive from you, including your name and any other identifying information, will be strictly confidential and kept under lock and key. Please keep in mind that these are only a sampling of the inclusion and exclusion criteria. There are other criteria, including the results of the screening blood work, that may make you ineligible for participation.

Do I have your permission to ask you these questions?

(If No): Thank you very much for calling.

(If Yes, ask the following questions):

(Date and time permission granted: _____; Interviewer signature: _____)

How old are you?

Must be between 18-45 years of age

The answers of these questions must be answered “Yes”:

Are you pregnant with one baby at this time?

Are you beyond 24 weeks’ of pregnancy?

Has your doctor recommended a 3-hour glucose test to check for diabetes during this pregnancy?

This question must be answered “No”: Are you taking any medications for the gestational diabetes yet?

Was everything normal on your baby’s ultrasound?

Do you have a history of diabetes outside of pregnancy?

Have you taken any steroids by mouth or through injection in the past 7 days?

Do you have an allergy to Glyburide, Metformin or Sulfa?

Do you have any significant hepatic disease?

Do you have congestive heart failure or a history of an MI?

Do you have any severe pulmonary disease?

Please check:

Volunteer is NOT ELIGIBLE to be screened for this study.

(If NOT ELIGIBLE): Thank you for your interest, but you are not eligible for this study. The information that I collected from you will be destroyed.

Volunteer is ELIGIBLE to be screened for this study.

(If ELIGIBLE): You are eligible to participate in the study. Would you like to schedule your first study visit?

(If No): Thank you for calling.

(If Yes): (Schedule the Volunteer)

Do you have any questions at this time?

[figure not shown]
Subject's Name: _____ Phone: _____

Date Scheduled: _____ Time of Appointment: _____
Phone Script reviewed by: _____

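### Decliner interviews number 15 in Aim 3 but 10 in the procedures, and the phone script's ultrasound item has no correct pass answer and is wider than the protocol exclusion

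*Combined protocol and SAP*

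**What the plan says.** **Interviews.** Aim 3 (II. Objectives) names three groups. The first is "pilot participants (n=16"), the second is 15 prenatal care providers, and the third is "women who are approached but decline to participate in the pilot study (n=15"). The interview paragraph in VII. Study Procedures, after Table 4, states: "16 participants (8 in each group) will be interviewed along with 10 women who decline to enroll in the study". It mentions provider perception but gives no provider number.

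**Ultrasound item.** The Screening Phone Script has a block of questions whose required answer is Yes. Next comes a singular heading, "This question must be answered" No, on the same line as the question about current medication for gestational diabetes. The ultrasound question ("Was everything normal on your baby"…) and six history questions follow with no new heading. The script warns callers that "these are only a sampling of the inclusion and exclusion criteria". The matching exclusion in III. Participants is "Major congenital anomaly with anticipated preterm delivery".

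**What happens after the call.** VI. Sample Size says the trial is introduced to every woman having an OGTT. At the Screening Visit (VII. Study Procedures), held at that test, "Her medical records will be reviewed" and eligibility is checked.

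**The concern.** The two matters are unrelated and should be handled separately.

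Interviews with decliners are the Aim 3 source on barriers to participation. With two targets in current text, and no amendment log to explain them, nobody can say when that part of Aim 3 is complete.

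The ultrasound item runs in the opposite direction to its neighbours. Seven questions around it are passed by answering No; a woman with a normal scan answers Yes. If the No heading runs on, a normal scan fails. If it covers only the medication question, the interviewer has no instruction for the ultrasound item. Even with Yes as the pass answer, any scan that is not entirely normal fails, although the protocol excludes only a much narrower group. Because feasibility is the trial's primary objective, a script that can turn away protocol-eligible women bears on the recruitment figures the pilot is meant to produce.

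**Working it through.** **Plan's own figure.** The only sample-size precision stated is a margin of at most 0.18 with 30 women per arm. At p = 0.5, 1.96 × √(0.5 × 0.5 / 30) = 0.179, so it reproduces. Neither item here affects it.

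**Interview count.**

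| Group | Aim 3 | Procedures |
|---|---|---|
| Participants | 16 | 16 (8 + 8) |
| Providers | 15 | no number given |
| Decliners | 15 | 10 |
| Total, providers kept at 15 | 16 + 15 + 15 = 46 | 16 + 15 + 10 = 41 |

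The gap is 15 − 10 = 5, one third of the Aim 3 number. The participant row agrees, so the procedures paragraph is not describing a different interview study. Its remark that the decliners must agree to be interviewed does not reconcile the two, since that is true of any interviewee.

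To show what the gap could mean, assume independent interviewees and a barrier held by a share p of decliners. The chance of hearing it at least once is 1 − (1 − p)^n. The values of p are assumptions; the documents give none.

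| p | n = 15 | n = 10 |
|---|---|---|
| 0.10 | 0.794 | 0.651 |
| 0.20 | 0.965 | 0.893 |
| 0.30 | 0.995 | 0.972 |

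The difference is noticeable for uncommon barriers and small for common ones.

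**Ultrasound item.** Questions from the No heading on: medication (1), ultrasound (1), and diabetes, steroids, allergy, hepatic, cardiac and pulmonary (6), making 8. One of the 8, ultrasound, has opposite polarity. The six history items are plain exclusion questions whose intended answer is clear from III. Participants.

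The item can be read three ways: No carries on from the heading; no answer is stated; or the interviewer infers Yes.

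| Caller | Protocol, this criterion | No carries on | No answer stated | Yes inferred |
|---|---|---|---|---|
| Scan entirely normal | not excluded | fails | undefined | passes |
| Minor finding | not excluded | passes | undefined | fails |
| Major anomaly, preterm delivery not expected | not excluded | passes | undefined | fails |
| Major anomaly, preterm delivery expected | excluded | passes | undefined | fails |

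No column agrees with the protocol in every row. The last comes closest, and still fails two groups that the protocol does not exclude. The script's caveat about sampling the criteria explains criteria it leaves out, not a question stricter than the criterion it represents.

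**The case against.** The strongest reply concerns the ultrasound item. The No heading is singular and shares a line with the medication question, so it most naturally covers that question alone. A sensible interviewer would take a normal scan as a pass, and could ask a follow-up before deciding. A broad lay question ahead of record review is ordinary practice. Layout lost from the PDF might also have shown answer columns. All of this stands as a reason not to insist on the reversed reading: a missing answer is at least as likely. It does not supply a correct pass answer, and it does not narrow the wording to the protocol's exclusion.

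A reader might infer that a woman wrongly turned away by phone is lost to the trial. The documents do not support that. Her OGTT is a clinical test recommended by her own physician, the trial is introduced to all women undergoing one, and records are reviewed there. She may therefore be approached again and found eligible. What remains is that she has already been told she is not eligible, and no section provides for re-approaching her.

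A reader might also infer, from the script's promise to destroy what ineligible callers said, that exclusion reasons for screened women are lost even though IV. Outcome Measures promises to track them. The documents point the other way. The script's tick box decides whether a caller may go on to be screened, and the Screening Visit takes place at the OGTT, so callers appear to come before the 300 screened. The script's title leaves slight doubt, but nothing shows that tracked reasons are destroyed.

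On the interview numbers, no reading makes 15 and 10 agree.

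**Conclusion.** Both inconsistencies hold on the text, and both are minor. The decliner target is 15 in one section and 10 in another, giving 46 or 41 interviews if the 15 providers stay. The ultrasound item has either no stated pass answer or a reversed one, and its wording is wider than the exclusion under any reading in which an abnormal scan fails.

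The harm from the script is a possibility, not a demonstrated loss. The documents do not give the share of women who enter by phone, how many would have a scan that is not entirely normal, or how staff would apply the item, so the number wrongly told they are ineligible is unknown and may be zero. No effect on the 300 screened, the 60 included or the 0.18 margin is claimed. The handling of ineligible callers' information is at most an unstated denominator.

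**What to change.** 1. Choose one decliner interview number and use it in both Aim 3 and the interview paragraph of VII. Study Procedures.
2. Give the ultrasound item its own answer heading, and word it to match the exclusion in III. Participants, covering both the major anomaly and the expected preterm delivery. State the pass answer that goes with the new wording.
3. Put the remaining history items under a plural heading saying that each must be answered No.
4. Optionally, add one sentence stating that phone callers lie outside the 300 screened, as the Screening Visit, Sample Size and script wording suggest. The destruction sentence needs no rewriting on this account.

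The cost is a minor ethics-board wording amendment to the script, one corrected number in the protocol and, if adopted, the sentence on callers. There are no added patients, visits or procedures.
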